validate these findings in a prospective cohort and to document prospectively whether untreated OSA worsens existing lung injury in patients with concomitant ILD. We will use a two-pronged approach to address this question: 1) We plan to recruit prospectively additional 78 patients with untreated moderate-to-severe OSA and assess the above biomarkers of alveolar endothelial injury before and after 4 weeks of clinically-initiated PAP therapy (not randomly allocated owing to the well-recognized societal hazard posed by untreated OSA patients with daytime somnolence). Using the effect size and SD estimates from the HeartBEAT and BestAir samples, a sample of 78 patients will provide 80% power to detect an effect of the size that we observed in **Aim 2** with $\alpha(2) = 0.05$; 2) We will recruit all participants as planned for **Aim 3** (anticipated 100 patients with ILD and concomitant OSA and 65 patients with ILD who do not have OSA) and compare their baseline levels of alveolar epithelial and endothelial injury biomarkers. This approach is crucial to establish whether patients with concomitant ILD and OSA have a greater degree of alveolar endothelial injury compared with ILD patients without OSA. If OSA turns out not to contribute independently to alveolar endothelial injury, this information would also be valuable considering that PAP may worsen existing alveolar endothelial injury in ILD patients, which suggest that alternative treatments for OSA that do not increase alveolar distension (for example, oral appliances) may be particularly suitable for patients with concomitant ILD and OSA. After validating our findings from Aim 2 as described above, we will explore in future studies whether oral appliances lower markers of AEC and endothelial injury in ILD patients with OSA.

Study Design

Aim 1: Determine whether the greater OSA severity is associated with higher levels of serum biomarkers of AEC and endothelial injury and ECM remodeling in community dwelling adults. We will perform cross-sectional analyses in this Aim.

Sampling frame and participants: We will sample participants from the MESA Sleep Study. We will sample the 1,830 MESA Sleep study participants who have available polysomnography data and no self-reported lung disease. We realize that a small proportion of participants will have missing or low-quality samples.

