Sampling frames and participants: Participants will be sampled from two completed clinical trials: the HeartBEAT and BestAIR trials. Each trial shares common design features and study eligibility criteria with a few exceptions, notably the timing of the measurement of the primary endpoint. Both were designed to test the hypothesis that active CPAP compared to a control intervention improves 24-hour blood pressure in patients with moderate-to-severe OSA and cardiovascular risk factors. The results of the HeartBEAT trial have been reported in the New England Journal of Medicine²³. It was a four-site, three-arm, parallel group, randomized trial of 12 weeks of CPAP, oxygen supplementation, or healthy lifestyle and sleep education for adults aged 45 to 75 years with moderate-to-severe OSA (AHI > 15/hr) and either²³ coronary artery disease or²⁴ three or more cardiovascular risk factors²³. Those with heart failure, a resting SpO₂ < 90%, any current use of supplemental oxygen, or current smoking were excluded. All HeartBEAT participants with available serum who were randomized to the CPAP arm or the healthy lifestyle and sleep education arm (n = 200) will be included in this Aim (those randomized to oxygen will not be included in this Aim). The BestAIR trial is a two-site,

randomized trial comparing active CPAP (with or without behavioral support for CPAP use) to control interventions (education with or without sham CPAP) over 6 to 12 months of follow-up²⁴. For the purpose of this analysis, all individuals receiving active CPAP will be compared to all individuals in the control arms. Inclusion criteria were similar to the HeartBEAT trial: age 45 to 75 years with moderate-to-severe OSA (AHI > 15/hr) with clinical heart disease, diabetes or >3 cardiovascular risk factors. All BestAIR participants will be included (n = 169).

Exposure measurement: We will use the original randomized allocation assigned in the two trials as our primary exposure. In both trials, participants were randomly assigned with equal probability to treatment arms using a stratified permuted block design with stratification by recruitment site and presence of coronary artery disease.

Outcomes: We will measure MMP-7, SP-D, SP-A, and Ang-2 in baseline and follow-up (3 months in HeartBEAT; 6 months in BestAIR) morning fasting sera using commercially available ELISA kits as described in Aim 1. These samples are already stored at the University of Vermont.

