This Aim 2 has been completed. We focused on BestAIR and HeartBEAT trials participants with moderate to severe OSA (AHI 15) who adhered with CPAP for 4 h daily. As this adherence level is averaged over all days, it is higher than the conventional clinical target of 4 hours/night for at least 5 nights/week, and was chosen because we expected the effect to be most pronounced in these patients. In addition, this planned “per protocol” analysis, restricting to individuals randomized to CPAP who used it for at least 4 hours/night based on objective monitoring, corresponds with our current Aim 3 study design. However, contrary to our hypothesis, the levels of four biomarkers of lung inflammation and extracellular remodeling were not reduced by effective PAP therapy in OSA patients. In fact, effective PAP therapy was associated with an increased circulating level of Ang-2, an endothelial growth factor considered a marker of acute lung injury.

Given the limited biospecimen resource, we re-evaluated the markers planned for analysis and decided to substitute osteopontin for SP-A, as a putative marker of fibrogenesis and ECM remodeling, and therefore likely to provide more valuable information than SP-A. SP-A had been identified as a marker of AEC injury; however, it was felt that SP-D is a better marker of the same domain, and the redundancy was not needed, especially considering limited biospecimen resources.

Revised Specific Aim 3: a) to determine prospectively whether clinically-initiated 4-week PAP therapy increases markers of alveolar endothelial lung injury in OSA. b) to determine whether untreated OSA promotes AEC and endothelial injury and ECM remodeling biomarkers in adults with ILD and OSA compared with those without OSA.

Study Design & Sampling Frame: We will perform a prospective study. We will sample participants from the New York Presbyterian/Columbia Pulmonary Fibrosis Foundation Care Center and from The Columbia University Center for Sleep Medicine.

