Selection Criteria, Expected Enrollment, and Screening: This study plans to enroll approximately 165 subjects with interstitial lung disease. We anticipate that 100 of those will have concomitant OSA and 65 will not have concomitant OSA. We will enroll 78 OSA patients from The Columbia University Center for Sleep Medicine and assess the above biomarkers of alveolar endothelial injury before and after 4 weeks of clinically-initiated PAP therapy (not randomly allocated owing to the well-recognized societal hazard posed by untreated OSA patients with daytime somnolence).

Inclusion Criteria for Patients with ILD:

1. Informed consent
2. Age 18 years or greater
3. Diagnosis of any of the following fibrotic interstitial lung diseases as defined by ATS/ERS/JRS/ALAT guidelines and research statements and Delphi surveys^{3, 4, 5}:
Idiopathic pulmonary fibrosis - Idiopathic non-specific interstitial pneumonia (NSIP) with fibrosis - Chronic hypersensitivity pneumonitis with fibrosis - Connective tissue disease related interstitial lung disease (CTD-ILD) - Unclassifiable idiopathic interstitial pneumonia with fibrosis

Exclusion criteria for Patients with ILD:

1. Clinically significant lung disease other than fibrotic interstitial lung disease
2. Planned change to the IPF treatment during the study period
3. Current cigarette smoking (past 4 weeks)

4. Lower respiratory tract infection in past 60 days. (Upper respiratory tract infection is not a contraindication)
5. History of life threatening cardiac arrhythmias
6. Known chronic heart failure (LVEF < 45% or echo evidence of RV dysfunction or PH)
7. Chronic opiate analgesic use
8. History of sleepiness-related automobile accident within past year of enrollment
9. Expected survival time in the opinion of the investigator of less than 6 months
10. History of stroke or spinal cord injury

Study Overview: After informed consent and review of inclusion/exclusion criteria, study participants will undergo full-night polysomnography at their baseline visit (see below).

Phlebotomy, spirometry, 6-minute walk test, diffusing capacity, and questionnaires completed at the research visit.

Inclusion criteria for OSA patients:

1. Age >18 years
2. Clinical diagnosis of untreated OSA documented by nocturnal polysomnography.

Exclusion criteria for OSA patients:

1. Current treatment with CPAP or oral appliance
2. Identical exclusion criteria as for ILD patients

STATISTICAL PROCEDURES

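### Aim 3a is recruited and sized as 78 patients with moderate-to-severe OSA, but the OSA inclusion list used for screening has no severity criterion

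*Combined protocol and SAP*

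**What the plan says.** The rationale for the revised Aim 3, in the Background, states the target population: "We plan to recruit prospectively additional 78 patients with untreated moderate-to-severe OSA". The sample size follows in the same paragraph: "Using the effect size and SD estimates from the HeartBEAT and BestAir samples, a sample of 78 patients will provide 80% power", for an effect of the size seen in Aim 2, at two-sided 0.05.

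The Aim 2 section describes where that effect came from. HeartBEAT enrolled adults aged 45 to 75 with an AHI above 15/hr, and BestAIR's criteria are given as similar: "age 45 to 75 years with moderate-to-severe OSA (AHI > 15/hr"). The account of the completed Aim 2 analysis says that it focused on "participants with moderate to severe OSA (AHI 15) who adhered with CPAP for 4 h daily". (The comparison sign before 15 appears to have been lost in text extraction and is not treated as an error.)

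The section headed Selection Criteria, Expected Enrollment, and Screening gives the number without the severity: "We will enroll 78 OSA patients from The Columbia University Center for Sleep Medicine". The inclusion list for OSA patients has two items, age over 18 and "Clinical diagnosis of untreated OSA documented by nocturnal polysomnography". The exclusions are current CPAP or oral appliance treatment plus the list used for ILD patients, and none of these mentions AHI or severity. Under Recruitment and Consent, all patients of the sleep center are screened, and those who meet the inclusion and exclusion criteria are telephoned.

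**The concern.** The sentence that justifies the sample size and the list that decides who is approached describe different cohorts. A coordinator who applies the list as printed can enrol a patient with mild OSA, whom the rationale does not include.

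This matters because Aim 3a is meant to validate the Aim 2 finding prospectively, and its 80% power is borrowed from Aim 2. If the enrolled cohort is broader than the one the power refers to, a reader of the results cannot tell which population was tested. Nor can the reader tell whether a null result speaks to the Aim 2 finding or to a different mix of patients.

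**Working it through.** **1. The plan's own figure.** The 78 cannot be reproduced forwards, because the Aim 2 effect size and SD are not printed. It can only be inverted. The documents name no test, so assume a paired before/after comparison:

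- Inputs from the Aim 3 rationale: n = 78, power 80%, two-sided alpha 0.05.
- Normal approximation: d = (1.960 + 0.842) / √78 = 2.802 / 8.832 = 0.317.
- Exact noncentral t: d = 0.321.

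This is the standardised change that the stated power implies. The documents give no value to compare it with, so it neither confirms nor refutes the 78.

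**2. The cohort, place by place.**

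| Place in the document | Severity stated |
|---|---|
| Background, central hypothesis | moderate-to-severe |
| Background, revised Aim 3: recruitment and power | moderate-to-severe, no AHI cut-off |
| Aim 2, source trials | moderate-to-severe, AHI above 15/hr |
| Aim 2, completed analysis | moderate to severe |
| Selection Criteria, enrolment sentence for the 78 | none |
| Inclusion criteria for OSA patients | none |
| Exclusion criteria for OSA patients | none |
| Recruitment and Consent, OSA-only cohort | OSA confirmed by polysomnography; no severity |

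The first four rows give the intent and the basis of the power. The last four control enrolment. The severity condition appears in the first group and is missing from the whole of the second.

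**3. Can the effect on power be calculated?** Let f be the share of enrolled patients with mild OSA, and r the effect in mild OSA relative to the effect in moderate-to-severe OSA. With the SD unchanged, the average standardised effect is d × [1 − f(1 − r)]. Neither f nor r is in the documents. To show how far the answer depends on them, assume f = 20%, d = 0.321 and n = 78:

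- r = 1: d stays at 0.321 and power at 80%.
- r = 0.5: d = 0.321 × 0.90 = 0.289, power 71%.
- r = 0: d = 0.321 × 0.80 = 0.257, power 61%.

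The spread comes entirely from the assumed r, and a different f would move it again. These are illustrations, not estimates of what Aim 3a has lost.

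**4. Other differences from Aim 2.** The Aim 2 patients were aged 45 to 75, had cardiovascular disease or risk factors, and were selected for CPAP use of 4 hours daily. They were measured at follow-up times of "3 months in HeartBEAT; 6 months in BestAIR". Aim 3a takes patients over 18, states no cardiovascular or adherence criterion, and measures at 4 weeks. The Aim 2 account nevertheless says that its per-protocol analysis "corresponds with our current Aim 3 study design". Aligning severity would remove one of these differences and leave the rest.

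**The case against.** The strongest reply is that the inclusion list is incomplete rather than contradictory. The enrolment sentence repeats the rationale's 78 patients, its biomarkers, its 4 weeks and its reason for not randomising, so it reads as a shortened restatement of the same cohort. Nowhere does the plan say that mild OSA is wanted. This stands as to intent. A reader might infer that the documents leave open which population is meant. They do not: the central hypothesis, the recruitment sentence and the Aim 2 population all point to moderate-to-severe OSA. The objection does not remove the problem, because screening follows the list and not the rationale.

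A second reply is that patients enter Aim 3a only if their own clinician starts PAP, which may tilt enrolment towards more severe disease. That is plausible, and the share with mild OSA could be small. It is still not a severity criterion. The investigators have no role in the decision to prescribe, and no severity threshold for prescribing is given.

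A third reply is that no harm has been shown. A reader might infer from the mismatch that Aim 3a is underpowered or that 78 is the wrong number. The documents do not support either inference. They do not show that mild OSA responds less, and they give none of the quantities needed to work out a loss.

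**Conclusion.** The inconsistency is real and should be fixed. The operative eligibility list admits a broader population than the one for which the sample size and the 80% power are stated. Confidence is high on that textual point, which rests on the printed criteria and needs no statistical assumption.

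The consequence for power is unquantified. It depends on the share of mild OSA and the effect in mild OSA, and both are absent. The range shown above assumes a paired test, an unchanged SD and an invented 20% share. The finding does not establish that 78 is too few. Nor would correcting severity alone secure the 80%, given the differences in age, cardiovascular risk, adherence and timing. What is lost for certain is a clear statement of which population Aim 3a tests.

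**What to change.** Reconcile the rationale for the revised Aim 3 with the inclusion criteria for OSA patients.

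- **If moderate-to-severe OSA is intended, as the documents suggest:** carry that criterion into the OSA inclusion list, with the sponsor confirming the AHI cut-off. The change is one line. The sample size and the stated power basis stay as they are. Recruitment would be somewhat slower, by an amount that cannot be estimated without the share of mild OSA among eligible patients.
- **If any severity is in fact intended:** correct the recruitment sentence in the rationale and state that the 80% power applies only to a moderate-to-severe cohort. Recruitment is unaffected, but the plan would then have no power statement for the cohort it enrols.

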Polysomnography: Participants with ILD will undergo home polysomnography (PSG) after they have consented to the study. We will use the Nox A1 sleep recorder manufactured by Nox Medical (Reykavik, Iceland) for the home PSG recordings. This will strictly be a research study and not meant for clinical purposes. PSG devices will be returned to Columbia and recordings uploaded by the research team. PSG exams will be transferred to and scored by the Brigham and Women's Sleep Reading Center (Boston, MA, USA) in accordance with the American Academy of Sleep Medicine Manual²⁸. Patients without ILD will be recruited from The Columbia University Center for Sleep Medicine after clinically indicated polysomnography.

Supplemental oxygen: If participants use supplemental oxygen while sleeping at baseline, they will use their supplemental oxygen as prescribed by their healthcare provider during the home PSG.

Phlebotomy and urine will be performed using methods previously used in MESA. Morning fasting blood with tourniquet time < 2 min. will be drawn. Mid-stream urine will be collected. The samples will be processed within 30 minutes and stored at -80°C.

Spirometry and DLCO will be performed by trained technicians in accordance with ATS/ERS guidelines in the MESA PFT lab in the CTSA and PFT lab in Herbert Irving Pavilion 3rd Floor.^{30, 31}

Questionnaires will be completed by participants. Questionnaires include Epworth Sleepiness Scale (ESS).^{32,37}

Demographic and clinical data (age, gender, race/ethnicity, smoking status, cigarette packyears, and medical history) will be ascertained using standardized questionnaires. Height and weight will be measured using a calibrated stadiometer scale. A board-certified pulmonologist will perform a standardized physical exam and record her or his findings in a pre-formatted form.

Clinical Data & Events: We will record clinical data, including, hospitalizations, exacerbations, and deaths.

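### Aim 3b concerns untreated OSA in ILD, but nothing in the ILD eligibility criteria, the home-PSG rules or the analysis keeps out or identifies patients already on CPAP or an oral appliance

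*Combined protocol and SAP*

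**What the plan says.** The revised Aim 3, part b, is "to determine whether untreated OSA promotes AEC and endothelial injury and ECM remodeling biomarkers in adults with ILD and OSA", compared with ILD patients who do not have OSA. The word untreated recurs in the Background, under Outcome measures and under Research Questions/Hypotheses.

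Under Selection Criteria, Expected Enrollment, and Screening, the OSA-only cohort is held to that condition twice. Inclusion item 2 requires "Clinical diagnosis of untreated OSA documented by nocturnal polysomnography", and exclusion item 1 is "Current treatment with CPAP or oral appliance". The ILD cohort has three inclusion items and, under "Exclusion criteria for Patients with ILD", ten exclusion items. None of the thirteen mentions CPAP, PAP or an oral appliance. The one item on treatment concerns changes to IPF therapy. A cross-reference links the lists in one direction only: the OSA-only list adopts the ILD exclusions.

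For the home PSG, the Supplemental oxygen paragraphs (in both Statistical Procedures and Study Procedures) say that patients on nocturnal oxygen "they will use their supplemental oxygen as prescribed by their healthcare provider during the home PSG". There is no matching sentence for PAP or an appliance. The analysis text for Aim 3b, in the Background, is a comparison of baseline biomarker levels between an expected 100 ILD patients with OSA and 65 without.

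**The concern.** The aim defines the exposure as untreated OSA, but following the plan as written admits treated patients. OSA status in the ILD cohort comes from the research PSG after consent, so a treated patient's group depends on whether the device was worn that night. On the device, the patient may be counted as no-OSA. Off it, the patient may be counted as untreated OSA. Neither is the stated contrast.

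This matters more here than in most studies because PAP is itself under suspicion. The Aim 2 summary reports that "effective PAP therapy was associated with an increased circulating level of Ang-2", among participants using CPAP for at least 4 hours, and Ang-2 is one of the Aim 3b markers. For the rest of the panel it says only that levels did not fall. The Background says "PAP may worsen existing alveolar endothelial injury in ILD patients" and intends to use Aim 3b to judge whether OSA contributes independently to injury, and hence whether non-PAP treatment may suit these patients. Unidentified PAP exposure would mix the two effects that the revised aim needs to separate.

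**Working it through.** **The textual check**

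| Where treatment status could be controlled | OSA-only cohort | ILD cohort |
|---|---|---|
| Inclusion criteria | Untreated OSA required (item 2) | Nothing |
| Exclusion criteria | CPAP or oral appliance (item 1) | Nothing in ten items |
| Cross-reference | Adopts the ILD exclusions | Does not adopt the OSA-only exclusions |
| Rule during PSG | Clinical PSG, not a study procedure | Oxygen only |
| Aim 3b analysis rule | Not applicable | None |

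**Illustrative size**

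From the documents: 100 v 65 for Aim 3b, and n = 78 with 80% power at two-sided 0.05 for Aim 3a. No effect size, SD or power is given for Aim 3b, so there is no stated power figure to reproduce. The number of treated patients *m*, the effect of treatment and the pre/post correlation ρ are assumptions. Power is from the noncentral t distribution, two-sided 0.05.

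*Benchmark.* Solving for 80% power with groups of 100 and 65 gives 0.449 SD. The normal approximation is close: (1.960 + 0.842) × √(1/100 + 1/65) = 0.446 SD.

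*Case 1: treated OSA patients classed as no-OSA, no PAP effect.* The groups become 100 − m and 65 + m. The difference becomes 0.449 − s·m/(65 + m), where s is the part of the OSA effect that remains despite treatment. If treatment removed the effect, s = 0. If it left the effect intact, s = 0.449. For m = 10 and s = 0.449, the difference is 0.449 × (1 − 10/75) = 0.389 SD.

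*Case 2: treated patients classed as untreated OSA, with treatment having removed the OSA effect.* The difference becomes 0.449 × (1 − m/100) with 100 v 65.

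| m | Case 1 power, s = 0.449 | Case 1 power, s = 0 | Case 2 difference | Case 2 power |
|---|---|---|---|---|
| 5 | 75% | 81% | 0.43 SD | 76% |
| 10 | 70% | 82% | 0.40 SD | 71% |
| 20 | 59% | 82% | 0.36 SD | 61% |

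With one patient moved, case 1 power is 79% to 80%.

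*Case 3: Ang-2 only, treated patients classed as untreated OSA and PAP raising the marker.* Read as a paired t test, n = 78 with 80% power implies a change of 0.321 SD of within-person change. On the between-person scale, with equal SDs before and after, this is 0.321 × √(2(1 − ρ)). The shift added to the contrast is m/100 times that.

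| ρ | Shift, between-person SD | m = 5 | m = 10 | m = 20 |
|---|---|---|---|---|
| 0.9 | 0.14 | 0.01 | 0.01 | 0.03 |
| 0.7 | 0.25 | 0.01 | 0.02 | 0.05 |
| 0.5 | 0.32 | 0.02 | 0.03 | 0.06 |

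Case 2 shrinks the contrast and case 3 enlarges it, so the net direction cannot be predicted.

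**The case against.** The strongest reply is that the aim and the outcome statement already say untreated, so a treated patient falls outside the contrast by definition. The Background also speaks of an inception cohort, and OSA status is assigned by a research PSG, both of which suggest mainly newly identified OSA. Medical history is collected by questionnaire and might capture treatment. These points make the problem less likely but do not close it. An aim does not screen patients, and for the OSA-only cohort the protocol did not rely on it. The inception-cohort phrase refers to patients diagnosed with OSA and is silent on treatment. No field for PAP or an appliance, and no use of one, is specified.

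The objections to size carry more weight. The counts of 5, 10 and 20 are invented, and the large losses need about 20 treated patients. Case 2 sits badly with the Aim 2 result, where effective PAP did not lower the markers. That result comes from OSA patients without known ILD, so it makes case 2 less likely without excluding it. Case 3 is small: at most 0.06 SD against 0.449 SD. It also carries the Aim 2 effect over to ILD.

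Recording status and then adjusting or stratifying would be another workable remedy. Leaving treated patients out also removes already-diagnosed OSA selectively, which is a reason to report the sensitivity analysis.

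**Conclusion.** The concern holds. The ILD eligibility criteria do not match the aim they serve, and neither the PSG procedure nor the analysis makes up for it. Confidence in this reading of the text is high.

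The consequence is uncertain. The documents give neither the number of treated ILD patients nor the effect of treatment on the markers in ILD. Under the stated assumptions, a handful of treated patients would do little. Twenty could take power from 80% to about 60% in the unfavourable cases, and the bias could go either way. The point should be fixed because, without recorded treatment status and an analysis rule, neither the absence of a problem nor its size could be shown afterwards.

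**What to change.** 1. Reconcile the ILD criteria with the aim by carrying the protocol's existing CPAP/oral-appliance exclusion into the ILD list.
2. For ILD patients already enrolled, record PAP and oral-appliance status at the blood draw and on the PSG night, alongside the medical history already collected.
3. State that treated patients are left out of the primary Aim 3b comparison.
4. Report a sensitivity analysis that adds them back in their PSG-assigned group.

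This takes one eligibility line, one data field and one analysis rule, and it changes no patient's care. If 5, 10 or 20 of the 100 OSA patients are left out and not replaced, power at 0.449 SD goes from 80% to 79%, 78% or 76%. If those left out were instead among the expected 65 without OSA, leaving 100 v 60, 55 or 45, it would be 78%, 76% or 70%.
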